6.3.1.2 Fasting Hyperglycemia

Fasting is defined as abstaining from food and drink (with the exception of water) for at least 8 hours. Dose modification guidelines for fasting hyperglycemia attributable to study treatment are outlined below and are intended to provide guidance for fasting glucose measurements assessed in the clinic. Decisions regarding study treatment should be made on fasting levels drawn in the clinic whenever possible.

Home glucose measurements may be used to trigger contact between patient and investigative site team and may lead to an unscheduled clinic visit to assess fasting glucose. Guidance for when to call the investigator/site staff (or designated endocrinologist, if applicable) should be provided to patients for hypoglycemia (e.g., glucose value under 70 mg/dL) and hyperglycemia (e.g., glucose value over 300 mg/dL). Alternative thresholds may be selected as clinically indicated per investigator discretion or institutional guidance and noted in the source documents. For any patients performing home glucose monitoring, the blood glucose log should be reviewed at each clinic visit (and source data retained), entry of results into the patient's eCRF will be limited to values which result in intervention.

In the event of ipatasertib interruption, anti-diabetic medications may need to be held or reduced (per investigator judgement) and glucose should be monitored closely to minimize the risk of hypoglycemia.

Severity of Fasting Hyperglycemia	Management Guideline
Fasting glucose value > ULN to 160 mg/dL (8.9 mmol/L)	
 Monitor fasting glucose per protocol Consider initiating home glucose monitoring
Fasting glucose value >160 to 250 mg/dL (> 8.9–13.9 mmol/L)	
 Interruption of ipatasertib until fasting hyperglycemia resolves to <160 mg/dL or better. Initiate home glucose monitoring Start oral anti-diabetic medications (e.g., metformin). If patient is already on an oral anti-diabetic medication, the dose of ipatasertib should be reduced by one dose level. If the patient previously has not been receiving any oral anti-diabetic medication, ipatasertib may be resumed at the previous dose level with initiation of oral anti-diabetic medication.
Glucose value 250 to 500 mg/dL (> 13.9–27.8 mmol/L)	
 Interrupt ipatasertib dosing until fasting hyperglycemia resolves to <160 mg/dL or better. Initiate home glucose monitoring Treat hyperglycemia as medically appropriate. Start (or increase

	
dose of) oral anti-diabetic medications (e.g., metformin).
 
 • Ipatasertib should be reduced by one dose level when treatment is restarted. • If hyperglycemia w/ a glucose value between 250-500 mg/dL recurs, permanently discontinue ipatasertib.
Glucose value > 500 mg/dL (> 27.8 mmol/L); life-threatening consequences	
 • Interrupt ipatasertib dosing until resolution to Grade 1 or better. • Treat hyperglycemia as medically appropriate. • Initiate home glucose monitoring • Start (or increase dose of) oral anti-diabetic medications (e.g., metformin). • Assess for volume depletion and appropriate intravenous or oral hydration. • Permanently discontinue ipatasertib.

6.3.1.3 Neutropenia and/or Thrombocytopenia

Addition of hematopoietic growth factors is allowed. If a dose delay is required as a result of neutropenia at any grade, patients should receive prophylactic granulocyte colony-stimulating factor or granulocyte-macrophage colony-stimulating factor per institutional standards. Patients should be counseled as to the risk of fever and infection and to the importance of contacting their treating physician or designee immediately if these conditions occur so that they can be promptly and appropriately managed. Dosage modification guidelines for neutropenia and/or thrombocytopenia attributable to ipatasertib are outlined below.

Severity of Neutropenia and/or Thrombocytopenia	Management Guideline
Grade 2	
 • Ipatasertib may be continued at the original dose.
Grade 3	
 • Ipatasertib should be held until recovery to Grade 1. Please see guidelines in this table regarding treatment for ongoing Grade 2 hematological toxicities. 
 ○ First episode: resume the original dose. ○ Recurrent episode: Ipatasertib should be reduced by one dose level when treatment is restarted. If patient has had recurrent Grade 3 neutropenia episodes on study, permanently discontinue ipatasertib. • Following a treatment hold of up to 4 weeks, if recovery to Grade 1 or better neutropenia does not occur, discontinue ipatasertib.
Febrile neutropenia and Grade 4 neutropenia	
 • Permanently discontinue ipatasertib treatment.

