6.1 Dose Delays/Dose Modifications

Unless otherwise noted in the dose modification tables below, treatment may be delayed \leq 28 days from the expected day of the next treatment for any reason. If treatment is delayed \leq 28 days subjects will proceed with the next cycle of treatment at the dose level recommended according to the tables below. Held or missed doses are not to be made up and will not alter the duration of total therapy prior to prostatectomy.

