Grade 3 Increase of \geq 7 stools per day over baseline; incontinence; hospitalization indicated; severe increase in ostomy output compared to baseline; limiting self-care ADL	
 Rule out infectious etiology. Treat per Grade 2 management guidelines and supportive care. Interrupt ipatasertib until diarrhea improves to Grade 1 or better. Ipatasertib should be reduced by one dose level when treatment is restarted. For recurrent Grade 3 diarrhea, reduce ipatasertib dose by one additional dose level. When study treatment is resumed, loperamide prophylaxis should also be resumed and continues as clinically indicated, if allowed by local guidance.

Severity of Diarrhea	Management Guideline
Grade 4 Life-threatening consequences; urgent intervention indicated	
 Rule out infectious etiology. Treat per Grade 2 management guidelines and supportive care. Permanently discontinue ipatasertib.

ADL = activities of daily living; BID = twice a day; QD = once a day.

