6.3.1.6 Pneumonitis

Pneumonitis is not known to be causally related to any of the study drugs; however, it has been observed with other drugs treating pathways similar to ipatasertib. Every effort should be made to determine the etiology of dyspnea and changes in pulmonary function.

Severity of Pneumonitis	Management Guideline
Grade 1	
 Continue study drugs. Perform CT scan and PFTs. Repeat CT scan every 8 weeks until a return to baseline.
Grade 2	
 If infectious etiology is ruled out or if improvement is not evident with broad spectrum antibiotics, prescribe corticosteroids as clinically indicated. Interrupt ipatasertib treatment until improvement to Grade 1 or better. Consider resuming ipatasertib at same dose level or one dose level below per investigator's assessment. Perform CT scan and PFTs. Repeat CT scan every 4 weeks until a return to baseline. For recurrent Grade 2 pneumonitis, discontinue ipatasertib. Discontinue ipatasertib if recovery to Grade 1 or better is not evident within 28 days.
Grade 3	
 If infectious etiology is ruled out or if improvement is not evident with broad spectrum antibiotics, prescribe corticosteroids as clinically indicated. Interrupt ipatasertib until improvement to Grade 1 or better. Resume ipatasertib at one dose level below previous dose per investigator's assessment. If recovery to Grade 1 or better is not evident within 28 days, discontinue study treatments. Perform CT scan and PFTs. Repeat CT scan every 4 weeks until a return to baseline. Bronchoscopy is recommended. For recurrent non-infectious Grade 3 pneumonitis events, ipatasertib should be permanently discontinued.
Grade 4	
 If infectious etiology is ruled out or if improvement is not evident with broad spectrum antibiotics, prescribe corticosteroids as clinically indicated. Permanently discontinue ipatasertib. Perform CT scan and PFTs. Repeat CT scan every 4 weeks until a return to baseline. Bronchoscopy is recommended.

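### For recurrent Grade 3 neutropenia, one table row calls for both a dose reduction on restart and permanent discontinuation of ipatasertib

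*Combined protocol and SAP*

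**What the plan says.** Section 6.3.1.3 covers two toxicities in one table: "Dosage modification guidelines for neutropenia and/or thrombocytopenia attributable to ipatasertib are outlined below". In the Grade 3 row ipatasertib is held until recovery to Grade 1, and what follows depends on whether the episode is the first.

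- First episode: "First episode: resume the original dose".
- Recurrence, first sentence: "Recurrent episode: Ipatasertib should be reduced by one dose level when treatment is restarted".
- Recurrence, second sentence, in the same sub-bullet: "If patient has had recurrent Grade 3 neutropenia episodes on study, permanently discontinue ipatasertib".

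A further bullet in the row deals with failure to recover: "Following a treatment hold of up to 4 weeks, if recovery to Grade 1 or better neutropenia does not occur, discontinue ipatasertib". The last row of the table, for febrile neutropenia and Grade 4 neutropenia, requires permanent discontinuation.

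Section 6.1 supplies no tie-breaker. After a delay of 28 days or less it sends the dosing decision back to the tables: "subjects will proceed with the next cycle of treatment at the dose level recommended according to the tables below".

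**The concern.** Both recurrence sentences are triggered by a recurrent Grade 3 event, and for neutropenia they lead to incompatible actions. An investigator with such a patient cannot tell from the page whether ipatasertib restarts one level lower or stops for good.

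Three things are at stake.

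- **Safety.** Decreased neutrophil count is a listed ipatasertib adverse event (Section 10.1.6), and two sites could handle the same event in opposite ways.
- **Exposure.** In Phase II the choice decides whether a man receives any more ipatasertib before prostatectomy, where the primary endpoint is read.
- **Recorded data.** Neutropenia is a selected adverse event for which grade, timing and interventions are collected (Section 11.1.6), and reasons for stopping protocol therapy go on the case report form (Section 6.4). Part of what is recorded would reflect how each site read the row.

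**Working it through.** The plan states no figure on this point, so the check is one of logic.

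**Step 1: a patient who meets both conditions.** Take a man on 400 mg daily. He has a Grade 3 neutropenia episode attributed to ipatasertib, recovers, and resumes the original dose as the first-episode line says. He then has a second Grade 3 neutropenia episode and recovers to Grade 1 within 4 weeks. The non-recovery bullet does not apply, and neither does the row for febrile or Grade 4 neutropenia. Only the two recurrence sentences are left.

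- The reduction sentence, with the dose levels in Section 6.3, has him restart at 300 mg.
- The discontinuation sentence has him receive no more ipatasertib.

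**Step 2: text elsewhere that might decide between them.** Section 6.1 refers back to the tables. Section 6.3 lists dose levels only. Section 6.4 lists grounds for stopping protocol therapy and does not mention recurrence of a toxicity. None ranks one sentence above the other.

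**Step 3: possible reconciling readings.** Two are reasonable, and neither is written down.

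| Event (each recovering to Grade 1 within 4 weeks) | By number: first recurrence reduces, later ones stop | By toxicity: recurrent thrombocytopenia reduces, recurrent neutropenia stops |
|---|---|---|
| Second Grade 3 neutropenia | Restart one level lower | Stop |
| Third Grade 3 neutropenia | Stop | Already stopped |
| Second Grade 3 thrombocytopenia | Restart one level lower | Restart one level lower |

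The readings disagree at the second Grade 3 neutropenia episode, which is the first point at which the recurrence rule is needed for neutropenia.

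**Step 4: comparison with other recurrence rules.** Other Grade 3 recurrence rules give a single action. For diarrhea (Section 6.3.1.1): "For recurrent Grade 3 diarrhea, reduce ipatasertib dose by one additional dose level". For pneumonitis (Section 6.3.1.6): "For recurrent non-infectious Grade 3 pneumonitis events, ipatasertib should be permanently discontinued". Where investigator choice is intended, as on resuming after Grade 2 diarrhea, the text says so. The neutropenia row does not, so it reads as a drafting slip and not as deliberate discretion.

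**Step 5: size.**

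- One man is 1/20 = 5% of planned Phase II enrollment, or 1/17 = 5.9% of the evaluable target. This is the weight of a single patient and not an estimate of frequency.
- Phase II treatment lasts 6 cycles of 28 days, 6 × 28 = 168 days. The ipatasertib in question for an affected man is whatever remains of that period.
- Phase I treatment continues until progression or unacceptable toxicity, so no such ceiling applies there.
- At 200 mg both sentences end ipatasertib, because Section 6.3 has no lower level. The restart-or-stop conflict therefore concerns men on 300 or 400 mg.

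**The case against.** The strongest reply is that the row is ambiguous but not contradictory. The reduction sentence is general and the discontinuation sentence names only neutropenia, so they can be read as a general rule and a specific one. The table also separates the two toxicities elsewhere, since its last row is about neutropenia alone. Alternatively, the reduction sentence speaks of an episode in the singular and the discontinuation sentence of episodes in the plural, which suggests a sequence. It can also be said that the reduction sentence only fixes the dose if treatment restarts and does not itself require a restart.

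These are fair readings, and the defect may be no more than a missing qualifier. They do not remove the problem, because the first two give opposite actions at the second Grade 3 neutropenia episode and the text favors neither. The toxicity reading also requires the general recurrence line to exclude neutropenia, although the table is headed for both conditions.

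The reply is right about size. The trigger is narrow: at least two Grade 3 episodes attributed to ipatasertib with recovery each time, and growth factor advised after any delay for neutropenia. The risk text in Section 6 gives no neutropenia frequency. If ipatasertib stops, darolutamide may continue under Section 6.4 and response is still assessed at prostatectomy. Discontinuation counts are not a listed endpoint. The weekly Phase I and monthly Phase II calls could align practice between sites, but they leave the text as it is.

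**Conclusion.** The concern holds. As written, a second Grade 3 neutropenia episode that recovers within the hold leads to two incompatible instructions in one sub-bullet, and nothing else in the protocol settles which applies. The conclusion rests on the wording alone and needs no assumption about event rates.

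How many patients it affects is unknown and may be few. Each affected man on 300 or 400 mg either continues one level lower or receives no more ipatasertib. The design's operating characteristics in Section 12.3 do not change. The point matters because it is a safety rule that careful investigators could apply in opposite ways, and it should be corrected. No view is taken on which instruction is clinically right.

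**What to change.** Reconcile the two sentences in the Grade 3 row of Section 6.3.1.3 so that each recurrent episode leads to exactly one instruction. The revised line should state whether neutropenia and thrombocytopenia are handled differently and which recurrence triggers which action. The choice of rule belongs to the sponsor and its clinical advisers.

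The cost is one line in the table, carried in an amendment and notified to sites. Nothing in the statistical design or sample size needs to change. If any patient has already had a recurrent Grade 3 neutropenia episode, the action taken should be noted so that the safety report can describe those cases consistently.

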6.3.1.4 Nausea and/or Vomiting

Dose reductions for nausea and/or vomiting should occur only if the symptoms persist despite a minimum of two treatments with adequate (combination) anti-emetic treatment(s), including ondansetron and other anti-emetics (i.e., prochlorperazine or metoclopramide per institutional guidelines).

Severity of Nausea and /or Vomiting	Management Guideline
Grade 1	
 Provide supportive care as needed.
Grade 2	
 Provide maximum supportive care as needed per local guidelines, with a minimum of two anti-emetics, including ondansetron.
Grade ≥ 3	
 Interrupt ipatasertib until nausea or vomiting resolves to Grade 2 or better. Provide maximum supportive care per local guidelines, with a minimum of two anti-emetics, including ondansetron. If Grade ≥ 3 nausea or vomiting recurs, ipatasertib should be reduced by one dose level when treatment is restarted.

6.3.1.5 Rash

Ipatasertib should be permanently discontinued for rash associated with Stevens-Johnson syndrome, toxic epidermal necrolysis, or other suspected severe hypersensitivity or allergic reaction. Dosage modification and symptom management guidelines for skin toxicity attributable to study treatment are shown in below.

Severity of Rash	Management Guideline
Grade 1	
 Continue study drugs. Consider topical corticosteroids.
Grade 2	
 Interrupt ipatasertib treatment until resolution to Grade 1 or better or the toxicity is no longer clinically significant. Treat rash with topical corticosteroids. Consider treatment of rash with oral corticosteroids.
Grade 3	
 Interrupt ipatasertib treatment until resolution to Grade 1 or better or the toxicity is no longer clinically significant. Treat rash with topical and systemic corticosteroids. Consider dermatological consultation. If the skin toxicity resolves to Grade 1 or better or is no longer clinically significant within 28 days, following completion of the steroid taper, ipatasertib may be resumed at one dose level below the previous dose. If recovery of the skin toxicity to Grade 1 or better does not occur or skin toxicity remains clinically significant continuously for 4 weeks, or Grade 3 rash recurs, permanently discontinue ipatasertib.

Severity of Rash	Management Guideline
Grade 4	
 Administration of systemic steroids (oral or intravenous) is recommended. Consider dermatological consultation and skin biopsy. Ipatasertib should be permanently discontinued.

6.3.1.6 Pneumonitis

Pneumonitis is not known to be causally related to any of the study drugs; however, it has been observed with other drugs treating pathways similar to ipatasertib. Every effort should be made to determine the etiology of dyspnea and changes in pulmonary function.

Severity of Pneumonitis	Management Guideline
Grade 1	
 Continue study drugs. Perform CT scan and PFTs. Repeat CT scan every 8 weeks until a return to baseline.
Grade 2	
 If infectious etiology is ruled out or if improvement is not evident with broad spectrum antibiotics, prescribe corticosteroids as clinically indicated. Interrupt ipatasertib treatment until improvement to Grade 1 or better. Consider resuming ipatasertib at same dose level or one dose level below per investigator's assessment. Perform CT scan and PFTs. Repeat CT scan every 4 weeks until a return to baseline. For recurrent Grade 2 pneumonitis, discontinue ipatasertib. Discontinue ipatasertib if recovery to Grade 1 or better is not evident within 28 days.
Grade 3	
 If infectious etiology is ruled out or if improvement is not evident with broad spectrum antibiotics, prescribe corticosteroids as clinically indicated. Interrupt ipatasertib until improvement to Grade 1 or better. Resume ipatasertib at one dose level below previous dose per investigator's assessment. If recovery to Grade 1 or better is not evident within 28 days, discontinue study treatments. Perform CT scan and PFTs. Repeat CT scan every 4 weeks until a return to baseline. Bronchoscopy is recommended. For recurrent non-infectious Grade 3 pneumonitis events, ipatasertib should be permanently discontinued.
Grade 4	
 If infectious etiology is ruled out or if improvement is not evident with broad spectrum antibiotics, prescribe corticosteroids as clinically indicated. Permanently discontinue ipatasertib. Perform CT scan and PFTs. Repeat CT scan every 4 weeks until a return to baseline. Bronchoscopy is recommended.

6.3.1.7 Mucositis

Mouthwash such as magic mouth wash (if inaccessible, warm salt or bicarbonate water) should be used as supportive care per institution guidelines. Brushing teeth after meals, keeping lips moisturized with

non-Vaseline® products, and avoiding alcohol, spicy food, and smoking have all been shown to reduce pain and infection related to mucositis. Ranitidine or omeprazole may be helpful if patients have epigastric pain.

Severity of Mucositis	Management Guidelines
Grade 1 or 2	
 Manage with maximum supportive care. If Grade ≥ 2 mucositis recurs in subsequent 4 week cycles, despite maximal supportive care, the dose of ipatasertib should be reduced by one dose level.
Grade ≥ 3	
 Hold ipatasertib until recovery to Grade 1 or better. If the mucositis resolves to Grade 1 or better during the current cycle, the dose of ipatasertib should be reduced by one dose level. If recovery of mucositis to Grade 1 or better does not occur within a maximum of 4 weeks, the patient will permanently discontinue ipatasertib.

6.3.1.8 Other Non-Hematologic Toxicities

- If other Grade ≥ 3 non hematologic toxicities not described above develop in patients, treatment with ipatasertib may be held, depending on the attribution of the toxicity, at the discretion of the investigator. During this time, treatment may continue with the other non-attributable treatment agent (darolutamide). Grade ≥ 3 non-hematologic toxicity should be monitored at least weekly.
- If the toxicity resolves to Grade 1 or better within 2 weeks, treatment may resume with the attributable agent.
- If the toxicity resolves to Grade 1 or better in 2–4 weeks, the dose of the attributable drug should be reduced by one level.
- Depending on the nature and the severity of the adverse event, if recovery to Grade 1 or better takes > 4 weeks, treatment may resume with the attributable agent with dose reduction, or the attributable agent may be permanently discontinued, at the discretion of the investigator.
- For Grade ≥ 3 toxicities associated primarily with laboratory abnormalities only (e.g., elevation of ALT, AST, lipase, or amylase, or decreases in phosphorus without clinical or other evidence of pancreatitis or other hepatic dysfunction), study treatment may continue without interruption and/or dose reduction at the discretion of the investigator per institutional practice. However, study treatment should be discontinued if the increase in ALT or ALT meets the criteria for “Hy’s law”:
 - ALT or AST $>8\times$ ULN
 - ALT or AST $>5\times$ ULN for more than 2 weeks
 - ALT or AST $>3\times$ ULN and TBL $>2\times$ ULN or INR >1.5
 - ALT or AST $>3\times$ ULN with the appearance of fatigue, nausea, vomiting, right upper quadrant pain or tenderness, fever, rash, and/or eosinophilia ($>5\%$)

6.4 Protocol Therapy Discontinuation

In addition to discontinuation from therapy related to toxicities as outlined in section 6.2.1, a subject will also be discontinued from protocol therapy and followed up per protocol under the circumstances

outlined below. The reason for discontinuation of protocol therapy will be documented on the electronic case report form (eCRF).

- Subject has received 6 cycles of study drugs (in the Phase II neoadjuvant cohort)
- Documented radiographic progression (Phase I or Phase II)
- The treating physician/designee thinks a change of therapy would be in the best interest of the subject
- The subject requests to discontinue protocol therapy, whether due to unacceptable toxicity or for other reasons
 - If a subject decides to prematurely discontinue protocol therapy (“refuses treatment”), the subject should be asked if he may still be contacted for further scheduled study assessments. The outcome of that discussion should be documented in both the medical records and in the eCRF.
- If protocol therapy is interrupted for ≥ 28 days from the expected day of the next treatment.

If ipatasertib is permanently discontinued due to toxicity, darolutamide may continue per protocol. If darolutamide is permanently discontinued due to toxicity, ipatasertib should also be discontinued and the patient should proceed to prostatectomy (Phase II).

